4.1.2 Method of assigning patients to treatment groups

Patients will receive a single dose of open label BI 655066 every 12 weeks. The initial dose for all patients moving into the open label extension study will be 90 mg.

If response is maintained, i.e. achievement of PASI₉₀ at Extended visit 2, 90 mg dosing will occur every 12 weeks until Extended EOT.

If there is a lack of response, defined as response below PASI₉₀ at Extended visit 2, the dose should be increased to 180 mg, and the 180 mg dosing will occur every 12 weeks until Extended EOT.

Detailed instructions for preparation of BI 655066 for administration of each dose will be given in the ISF.

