- Inclusion criteria 3 (Negative serum β -Human Chorionic Gonadotropin (β -HCG))
Exclusion criteria 8 (Any clinically significant laboratory abnormalities)

Check consistency in medical history with the data obtained at visit 1 of the previous trial. All changes in medical history must be documented as adverse events and will be followed up as such during this trial.

Re-record ongoing adverse events/concomitant medications from the previous trial and record any adverse events/concomitant medications that may have started between the two trials, in the event that the 6 week time-window between trials was used.

All patients will be administered 90 mg BI 655066 s.c. at Extended visit 1.

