### **Compliance**

There will be a summary of the number of subjects receiving study drug and dose at each study drug administration visit. This will be repeated on the cumulative number of doses.

When computing compliance at each study drug administration visit, the denominator will include all subjects who have not prematurely discontinued the study drug prior to the scheduled study drug injection. Subjects who have prematurely discontinued the study drug but have not prematurely discontinued the study are not used in the denominator.

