### **11.2 Analysis of Adverse Events**

#### **11.2.1 Treatment Emergent Adverse Events**

Treatment emergent adverse events (TEAEs) are defined as any event with an onset that is after the first dose of risankizumab in this study and with an onset date within 105 days after the last dose of study drug in the analysis period.

Events where the onset date is the same as the study drug start date are assumed to be treatment emergent, unless the adverse event start time is prior to the study drug start time. If an incomplete onset date is collected for an adverse event, the event will be assumed to be treatment-emergent unless there is other evidence that confirms that the event is not treatment-emergent (e.g., the event end date is prior to the study drug start date).

The number and percentage of subjects experiencing treatment-emergent TEAEs will be tabulated using the Medical Dictionary for Drug Regulatory Activities (MedDRA®) system organ class and preferred term.

Considering the fact that some subjects had dose escalation due to lack of efficacy at EV2, selected safety tables will be generated breaking down by the group of subjects who remained at 90 mg throughout the study, the group of subjects who received 180 mg at EV2, and total.

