**Summary tables will be presented as follows:****1. Adverse Event Overview**

The number and percentage of subjects experiencing treatment-emergent adverse events will be summarized for the following adverse event categories:

- Any TEAE
- Any TEAE with reasonable possibility of being related to study drug
- Any treatment emergent severe adverse event
- Any treatment emergent serious adverse event (SAE)
- Any SAE with reasonable possibility of being related to study drug
- Any TEAE leading to discontinuation of study drug.
- Any TEAE results in death.
- All death

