#### 4. Adverse Event per 100 Patient-years of Exposure

Adverse events occurring during the entire study will be presented by event rate per 100 patient-year.

AEs per 100 patient-years of exposure is defined as the number of AEs divided by the total exposure in 100 patient-years. Note that one event per preferred term per day per subject will be counted in the calculation of the number of AEs (i.e., a preferred term will not be counted twice on the same day for the same subject). See the calculation method below.

$$100 \times \frac{\text{Number of TEAEs}}{\text{Total Patient Years}}$$

where total patient years is defined as the sum of the study drug exposure (defined as date of last dose – date of first dose + 105 days (5 half-lives)) of all subjects normalized by 365.25, and rounded to one decimal place.

The following summaries of AEs per 100 patient-years of exposure will be generated:

- Adverse event overview
- TEAE by SOC and PT
- SAE
- Treatment emergent adjudicated CV events
- Treatment emergent malignancies
- Serious treatment emergent malignancies

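### Safety tables split by the dose given at EV2 count events from the first dose in this study, so they do not isolate experience after a 180 mg dose

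*SAP*

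**What the plan says.** SAP 11.2.1 gives a reason for a split by dose, "Considering the fact that some subjects had dose escalation due to lack of efficacy at EV2", and then breaks selected safety tables into "the group of subjects who remained at 90 mg throughout the study, the group of subjects who received 180 mg at EV2, and total". It does not list those tables. The same section defines a TEAE as "any event with an onset that is after the first dose of risankizumab in this study", with onset up to 105 days after the last dose in an analysis period that the SAP does not define.

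Every patient begins on the lower dose. Protocol 4.1.2 states: "The initial dose for all patients moving into the open label extension study will be 90 mg". Protocol 6.2.2.1 repeats it for the first extended visit: "All patients will be administered 90 mg BI 655066 s.c. at Extended visit 1". The increase to 180 mg is decided at EV2, nominally 12 weeks later, for patients below PASI 90.

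For event rates, SAP 11.2.1 item 4 says that "total patient years is defined as the sum of the study drug exposure". Each subject contributes one undivided span: last dose minus first dose, plus 105 days. The adverse event overview (item 1) includes the row "Any TEAE leading to discontinuation of study drug".

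Two other displays bear on the point. SAP 9.0 summarises how many subjects received drug, and at what dose, at each dosing visit, and adds: "This will be repeated on the cumulative number of doses". SAP 11.2.2 lists deaths, SAEs and adverse events (AEs) that led to stopping study drug.

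**The concern.** Column membership is fixed by what happens at EV2, but counting starts earlier, at the first dose in this study. No section restarts the count at EV2, divides person-time there, or limits the split to subjects who reached EV2. Two consequences follow.

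1. An event on 90 mg before EV2, in a subject who is later escalated, is counted in the 180 mg-at-EV2 column.
2. A subject must remain on treatment until EV2 to enter that column. Earlier stops cannot appear in it, whatever their cause. This is the familiar immortal-time problem.

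The SAP offers the split because of the escalation, and Protocol 4.1.3 ties the 180 mg dose to obtaining safety data at or above the proposed marketed dose. Readers will therefore look to this column for experience on 180 mg. No planned table gives events or patient-years counted from the first 180 mg dose.

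**Working it through.** The documents give no figure on this point, so there is none to reproduce. They also do not give the number escalated, the number of early stops or the event rates; values for these are assumptions.

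**Inputs**
- EV1 to EV2: 12 weeks = 84 days (Protocol flow chart).
- Exposure per subject: last dose − first dose + 105 days (SAP 11.2.1 item 4). I take the first dose to be the first in this study, to match the TEAE definition.
- Follow-up: the amendment that introduced the Extended dosing period is dated 10 June 2015 (Protocol section 11). After 1 May 2018 the next visit is the last (Protocol 3.1). That is 1,056 days, or 12 full 84-day intervals (12 × 84 = 1,008 days), so week 144 is a long-follow-up case. Week 48 serves as a short case.
- The flow chart runs to week 204 (day 1428). I do not use it: reaching it would need local approval of the transition about a year late (1,428 − 1,056 = 372 days).

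**Step 1: share of exposure before EV2, no dosing before EV1**

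Share = 84 / (days from EV1 to last dose + 105)
- Week 144: 84 / (1,008 + 105) = 84 / 1,113 = 7.5%
- Week 48: 84 / (336 + 105) = 84 / 441 = 19.0%

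**Step 2: effect on a rate ratio, if the patient-year tables are split**

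Apparent ratio = share × 1 + (1 − share) × R, where R is the true ratio.
- R = 2 (assumed): 2 − 0.075 = 1.92 at week 144; 2 − 0.190 = 1.81 at week 48.
- R = 1: the result is 1. The overlap dilutes a difference but does not create one.

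**Step 3: a whole column, with assumed follow-up**
- 80% reach week 144 and 20% stop at week 48: mean exposure 0.8 × 1,113 + 0.2 × 441 = 978.6 days; share 84 / 978.6 = 8.6%; ratio 1.91.
- If half also had 24 weeks (168 days) in this study before EV1, the mean lead-in is 84 days: share (84 + 84) / (978.6 + 84) = 168 / 1,062.6 = 15.8%; ratio 1.84. Some of that lead-in may be off-treatment follow-up.

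**Step 4: patient-years per escalated subject, from the EV2 dose versus from the first dose**
- Week 144: (1,008 − 84 + 105) / 365.25 = 2.82 versus 1,113 / 365.25 = 3.05
- Week 48: (336 − 84 + 105) / 365.25 = 0.98 versus 441 / 365.25 = 1.21

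**Step 5: stops before EV2**

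On the natural reading these subjects are in the 90 mg column. With an assumed 50 to 90 subjects there, each stop for an AE adds 1/50 = 2.0 to 1/90 = 1.1 percentage points to that column and zero to the other.

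An illustration with no dose effect: 100 subjects, the same constant hazard of AE discontinuation at both doses (0.05 per year), follow-up to 1,113 days, and 30% of those reaching EV2 escalated.
- Stops before EV2: 100 × (1 − exp(−0.05 × 84/365.25)) = 1.14, leaving 98.86.
- Risk after EV2: 1 − exp(−0.05 × 1,029/365.25) = 13.14%. This is the 180 mg column.
- 90 mg column: (1.14 + 0.7 × 98.86 × 0.1314) / (100 − 0.3 × 98.86) = 14.55%.

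The columns differ by 1.4 points although the doses do not. At hazards of 0.02 and 0.10 per year the pairs are 6.10% versus 5.48% and 26.98% versus 24.55%.

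**The case against.** The strongest reply is that the SAP defines groups of subjects by treatment path, not by dose at onset, and labels them correctly. Both columns start at the same point. With no dosing before EV1, 81.0% to 92.5% of an escalated subject's exposure follows the EV2 dose (100% less the shares in step 1). The analysis is descriptive, with no test. The groups are selected by response, so no recount makes the comparison causal. SAP 11.2.2 lists every death, SAE and AE discontinuation. The dilution figures matter only if the patient-year tables are among those split, which the SAP does not say. Nor does it say where subjects without an EV2 dose are placed.

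Most of this stands, and it limits the point. A reader might infer that the column is mislabelled, or that it says nothing about 180 mg. The documents support neither: the label is accurate and most of the exposure in the column is likely to follow EV2. What the text supports is that the split does not isolate that experience.

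The reply does not remove the second consequence. A subject without an EV2 dose cannot have received 180 mg at EV2, and has had only 90 mg in this study, so the 90 mg column is the only one of the two that fits. Individual listings do not correct a percentage in a summary table.

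**Conclusion.** The point holds in this limited form and should be corrected in the SAP. The 90 mg experience in the 180 mg-at-EV2 column is a modest dilution: 7.5% of exposure at week 144 and 19.0% at week 48 without lead-in, more for subjects dosed before EV1. It turns an assumed doubling into 1.92 or 1.81 and creates no difference by itself.

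The exclusion of pre-EV2 stops from the 180 mg group is different in kind. It can create a difference with no dose effect, chiefly in the AE-discontinuation rows, and it makes the 90 mg column look worse. Its total size is unknown; the per-stop figures rest on an assumed 50 to 90 subjects in that column and on the natural reading of where early stops are placed.

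A reader might also infer that the primary safety assessment is compromised, or that a 180 mg risk would be hidden. The documents do not support that: the Total column is unaffected by the split, and the dilution is modest with long follow-up.

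**What to change.** Keep the existing subject-group tables and the Total column. In the SAP:

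- For each split table, add a version restricted to subjects dosed at EV2, with TEAEs and person-time in both groups counted from the EV2 dose to the last dose + 105 days. Apply the existing same-day onset rule to the EV2 dose.
- Show events and discontinuations before EV2 separately, for all subjects.
- Report patient-years from the first 180 mg dose.
- State where subjects without an EV2 dose are placed. Name the split tables, say whether the patient-year tables are among them, and define the analysis period.
- Footnote the existing tables: counts in the 180 mg-at-EV2 group include time on 90 mg.

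The cost is SAP wording and a few extra descriptive tables; the planned analyses already need the dosing and onset dates. One limitation remains: because the 105-day window is longer than the 84-day dosing interval, some events after EV2 may reflect carry-over from earlier 90 mg dosing. The display stays descriptive, since the groups are selected by response.

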**Summary tables will be presented as follows:****1. Adverse Event Overview**

The number and percentage of subjects experiencing treatment-emergent adverse events will be summarized for the following adverse event categories:

- Any TEAE
- Any TEAE with reasonable possibility of being related to study drug
- Any treatment emergent severe adverse event
- Any treatment emergent serious adverse event (SAE)
- Any SAE with reasonable possibility of being related to study drug
- Any TEAE leading to discontinuation of study drug.
- Any TEAE results in death.
- All death

**2. Adverse Events by System Organ Class and Preferred Term**

TEAEs will also be summarized and presented using primary Medical Dictionary for Regulatory Activities (MedDRA) system organ classes (SOCs) and preferred terms (PTs). The SOCs will be presented in alphabetical order, and the PTs will be presented in alphabetical order within each SOC.

Subjects reporting more than one adverse event for a given MedDRA preferred term will be counted only once for that term (most severe incident for the severity tables and most related incident for the relationship tables). Subjects reporting more than one type of adverse event within a SOC will be counted only once for that SOC. Subjects reporting more than one type of adverse event will be counted only once in the overall total.

In addition, the number and percentage of adverse events events with causal relationship between the events and the study drug will be summarized using the same conventions described above.

### **Adverse Events by Maximum Severity**

The severity grading of AEs follows Rheumatology Common Toxicity Criteria (RCTC).

- Grade 1 – mild
- Grade 2 – moderate
- Grade 3 – severe
- Grade 4 – life threatening

Adverse events will also be summarized by maximum severity. If a subject has an adverse event with unknown severity, then the subject will be counted in the severity category of "unknown," even if the subject has another occurrence of the same event with a severity present. The only exception is if the subject has another occurrence of the same adverse event with the most extreme severity – ("Life-threatening"). In this case, the subject will be counted under the "Life-threatening" category.

The following summaries of TEAEs by SOC and PT will be generated:

- Any TEAE
- Any TEAE with causal relationship to study drug
- TEAE by maximum severity

In addition, summary of AEs by PT and by decreasing frequency of risankizumab total will be generated.

### **3. Areas of Safety Interest (ASI):**

ASIs will be summarized and presented using ASI Grouping and PT. ASI groupings are listed in [Table 2](#). These events are of interest due to a higher rate in the moderate to severe Ps population, or of interest for all Ig products or products in general (DILI).

The final list will be based on the most updated final version of risankizumab Product Safety Statistical Analysis Plan, which is consistent to the most updated risankizumab Risk Management Plan.

**Table 2. Areas of Safety Interest**

ASI Grouping	Categories (ASI)	Search Criteria	Terms to Display	Include in AE Overview (Y/N)
Adjudicated CV Events	Major adverse cardiovascular events (MACE)	Adjudicated events	
Display underlined terms defined by the following adjudicated terms:
 
 
• CV Death which includes CETERM values: Fatal CV, Fatal PE, Fatal Non-Cardiac/Non-Neuro Arterial Thrombosis/Thromboembolism, Undetermined Death, Not assessable death (cardiac/neuro/thrombotic), Fatal Stroke
 
• Myocardial infarction
 
• Stroke
 
	Y
	Extended MACE	Adjudicated events	
Display underlined terms from MACE and underlined terms below:
 
 
• Hospitalization for Unstable Angina
 
• Coronary Revascularization Procedures
 
	N
	Other CV events	Adjudicated events	
Display underlined terms defined by the following adjudicated terms:
 
 
• Thrombotic events which includes CETERM values: Deep Vein Thrombosis, TIA, Pulmonary Embolism, Non-fatal Non-Cardiac/Non-Neurological Arterial Thrombosis/Thromboembolism, Other Venous Thrombosis, specified (non-fatal)
 
• Cardiac arrhythmia which includes CETERM of: Clinically Significant Arrhythmia
 
• Congestive heart failure which includes CETERM of Heart Failure
 
• Hypertensive emergency
 
	N

**Table 2. Areas of Safety Interest (Continued)**

ASI Grouping	Categories (ASI)	Search Criteria	Terms to Display	Include in AE Overview (Y/N)
Serious infections, TB, fungal and opportunistic infections (including herpes zoster)	Serious infections	Serious PTs of the CMQ (company MedDRA query) Infections (CMQ 80000018)	PTs	Y
	TB	Tuberculosis (including Investigations) CMQ (code 80000033)	PTs	Y
	Opportunistic infections	Opportunistic infections CMQ (code 80000073)	PTs	N
	Fungal infections	Fungal infections CMQ (code 80000063)	PTs	N
	Herpes Zoster	Herpes zoster CMQ (code 80000175)	PTs	N
Malignancies	All possible malignancies	Narrow - Malignancies (SMQ 20000090)	PTs	N
	Malignant Tumours	Narrow - Malignant tumours (SMQ 20000194)	PTs	Y
	Non-melanoma skin cancer (NMSC)	Broad - Skin malignant tumours (SMQ 20000204) excluding terms identified by the Melanoma CMQ (code 80000119)	PTs	N
	Malignant Tumours excluding NMSC	'Malignant Tumours excluding NMSC' is identified by the 'Malignant Tumours' search excluding terms identified by the 'Non-melanoma skin cancer (NMSC)' search.	PTs	Y

**Table 2. Areas of Safety Interest (Continued)**

ASI Grouping	Categories (ASI)	Search Criteria	Terms to Display	Include in AE Overview (Y/N)
Hypersensitivity Reaction	Hypersensitivity	Narrow - Hypersensitivity (SMQ 20000214)	PTs	Y – serious events only
	Anaphylactic Reaction	Narrow - Anaphylactic reaction (SMQ 20000021)	PTs	N
Hepatic Events	Hepatic Events	Broad - Hepatic failure, fibrosis and cirrhosis and other liver damage-related conditions (SMQ 20000013) Broad - Hepatitis, non-infectious (SMQ 20000010) Broad - Cholestasis and jaundice of hepatic origin (SMQ 20000009) Broad - Liver related investigations, signs and symptoms (SMQ 20000008) Narrow - Liver-related coagulation and bleeding disturbances (SMQ 20000015)	PTs	N

#### 4. Adverse Event per 100 Patient-years of Exposure

Adverse events occurring during the entire study will be presented by event rate per 100 patient-year.

AEs per 100 patient-years of exposure is defined as the number of AEs divided by the total exposure in 100 patient-years. Note that one event per preferred term per day per subject will be counted in the calculation of the number of AEs (i.e., a preferred term will not be counted twice on the same day for the same subject). See the calculation method below.

$$100 \times \frac{\text{Number of TEAEs}}{\text{Total Patient Years}}$$

where total patient years is defined as the sum of the study drug exposure (defined as date of last dose – date of first dose + 105 days (5 half-lives)) of all subjects normalized by 365.25, and rounded to one decimal place.

The following summaries of AEs per 100 patient-years of exposure will be generated:

- Adverse event overview
- TEAE by SOC and PT
- SAE
- Treatment emergent adjudicated CV events
- Treatment emergent malignancies
- Serious treatment emergent malignancies

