2.2 TRIAL OBJECTIVES

The overall purpose of this open label extension (OLE) trial is to assess long-term safety and efficacy (durability of response) of BI 655066 in patients with moderate to severe chronic plaque psoriasis. In addition, this study will provide an opportunity for subjects to have extended access to a proven active therapy for approximately four years administration.

The primary objective of the study is to investigate safety of BI 655066, in patients with moderate to severe chronic plaque psoriasis, receiving long-term treatment.

Additional objectives of this study are to further investigate long-term efficacy, tolerability, pharmacokinetics, pharmacodynamics and immunogenicity of BI 655066.

Study endpoints are listed in [Section 5](#).

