3.3 SELECTION OF TRIAL POPULATION

Eligible patients from trial 1311.2 will be offered participation in this OLE trial. The check for patient eligibility will be based upon a successful completion (cf. [Section 3.3.2](#)) of the previous trial and on signing the Informed Consent for the OLE.

A 40 % dropout rate from preceding trial is expected, leaving approximately 100 patients to be entered in this trial.

A log of all patients included into the study (i.e. having given informed consent) will be maintained in the ISF at the investigational site.

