7.2 NULL AND ALTERNATIVE HYPOTHESES

The primary hypothesis is that BI 655066 will sustain effectiveness without emergent safety issues during the extended visit period. This will be characterized descriptively. There is no formal statistical hypothesis testing in this study.

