7.3.1 Primary analyses

The achievement of PASI90 at week 48 in the Extended dosing period is the primary efficacy endpoint, which is a binary variable.

For primary safety, the overall incidence rates of AEs, drug related AEs, and SAEs will be calculated.

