7.6 DETERMINATION OF SAMPLE SIZE

The sample size is determined by the completion of previous trial and the consenting for the extension.

Proprietary confidential information.

© 2018 Boehringer Ingelheim International GmbH or one or more of its affiliated companies. All rights reserved.

This document may not - in full or in part - be passed on, reproduced, published or otherwise used without prior written permission.

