### **4.0                   Study Objectives, Design and Procedures**

#### **4.1                   Primary Study Objective**

The primary objective of this study is to investigate long-term safety and efficacy of risankizumab during open-label treatment in patients with moderate to severe chronic plaque psoriasis.

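### The SAP plans 95% intervals for every efficacy percentage and mean but none for any adverse event result, and no first-event rates, so low counts of rare events carry no statement of what they exclude

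*SAP*

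**What the plan says.** Protocol 2.2 ranks safety first ("The primary objective of the study is to investigate safety of BI 655066") and efficacy below it ("Additional objectives of this study are to further investigate long-term efficacy"). SAP 4.1 instead names both together: "to investigate long-term safety and efficacy of risankizumab during open-label treatment". Protocol 7.2 states the hypothesis: "The primary hypothesis is that BI 655066 will sustain effectiveness without emergent safety issues during the extended visit period". It adds that this is to be described and not tested.

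For the primary safety analysis, Protocol 7.3.1 says that "the overall incidence rates of AEs, drug related AEs, and SAEs will be calculated". The SAP implements this in two ways:

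- **Subject counts and percentages** (SAP 11.2.1, items 1 to 3), with selected tables split into patients who stayed on 90 mg, patients given 180 mg at EV2, and total.
- **Event rates** (SAP 11.2.1, item 4): "Adverse events occurring during the entire study will be presented by event rate per 100 patient-year". The numerator counts a preferred term at most once per subject per day. The denominator is last dose minus first dose plus 105 days, summed over subjects.

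Neither carries an interval. SAP 10.1, which covers efficacy only, plans 95% intervals for percentages and means and also states that no tests are done.

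The protocol also plans time to AESI (7.1 and synopsis), Kaplan-Meier curves and cumulative event rates (7.3), and time to first onset of AESIs (7.3.3). SAP Section 11 contains none of these.

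**The concern.** The hypothesis includes an absence: no emergent safety issues. For an absence, the informative number is the upper limit of what the data leave possible, and the plan does not produce it.

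The two planned measures also leave a gap between them. A subject percentage gives a patient followed for one dose the same weight as one followed for several years. An event-count rate adjusts for exposure but lets one patient with a recurrent event contribute many times. Neither is a rate of first occurrence over time at risk, and the protocol's time-to-event summaries, which would have come closest, are missing from the SAP.

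At stake is how a report of zero or one MACE, malignancy or serious infection in about 100 patients will be read. Without an upper limit, it can look more reassuring than the data allow.

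**Working it through.** **The plan's own figure.** There is no power or precision calculation to reproduce. Protocol 7.6 says "The sample size is determined by the completion of previous trial and the consenting for the extension", and Protocol 3.3 says "A 40 % dropout rate from preceding trial is expected, leaving approximately 100 patients to be entered in this trial". The second implies 100 / 0.60 = about 167 patients in the preceding trial. The documents do not give that trial's size, so this can be neither confirmed nor refuted. I take n = 100.

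**Exposure.** Patient-years in this trial are not stated. I use the SAP formula, (last dose − first dose + 105) / 365.25, assuming 100 patients who all take their last dose at the same extended-period visit and counting from EV1:

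- Week 48: (336 + 105) / 365.25 = 1.207 years each, 120.7 PY in total.
- Week 192: (1344 + 105) / 365.25 = 3.967 years each, 396.7 PY.
- Week 204: (1428 + 105) / 365.25 = 4.197 years each, 419.7 PY.

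The last two assume no dropout, so they are upper bounds for the charted schedule.

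**Zero events, rate scale.** The two-sided 95% exact Poisson upper limit is −ln(0.025) / PY = 3.689 / PY.

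| PY (assumed) | Upper limit per 100 PY |
|---|---|
| 121 | about 3.1 |
| 200 | 1.84 |
| 300 | 1.23 |
| 397 | 0.93 |
| 420 | 0.88 |

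For comparison, two first events in an assumed 300 PY give 0.67 per 100 PY, with limits 0.08 and 2.41, a roughly 30-fold range.

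**Zero cases, percentage scale.** The Clopper-Pearson upper limit is 1 − 0.025^(1/n). For 0 of 100 it is 3.62%. For 1 of 100 the interval is 0.03% to 5.45%. The size of the 180 mg group is not stated. For assumed sizes of 10, 20 and 30, zero cases leaves 30.8%, 16.8% and 11.6% open.

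**How often zero would be seen anyway.**

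- With 100 patients and a true risk of 1%, 0.99^100 = 37%. With 2%, 0.98^100 = 13%.
- At an assumed true rate of 0.5 per 100 PY, exp(−0.005 × PY) = 14% at 400 PY and 37% at 200 PY.

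**The case against.** The best case for leaving the plan alone is that the trial is openly descriptive. Protocol 3.2 concedes that no powered or controlled analysis is possible, and Protocol 7.2 and SAP 6.0 rule out testing. For a rare event, a reader given the count and the patient-years can compute an exact interval. When events are few, repeats are fewer, so the event rate and the first-event rate nearly coincide. The subject-level tables would also expose a rate driven by one patient.

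Much of this stands, and it makes the point a reporting improvement rather than an error in a stated figure. It does not remove the point. An interval is estimation, not a test, and SAP 10.1 plans intervals for efficacy while also excluding tests. For SAEs and drug-related AEs, where repeats are more likely, first-event rates cannot be recovered from the planned tables.

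Three stronger readings are tempting, and the documents do not support them:

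- **That the intervals go only to secondary efficacy results.** SAP 10.1 covers all efficacy results, including PASI90 at week 48, which Protocol 5.1.1.1 calls the primary efficacy endpoint.
- **That zero counts undermine the primary safety results as a whole.** The primary safety endpoints (Protocol 5.2.1.1) include the occurrence of any AE, and a zero count there over years of treatment is not realistic. The figures above concern rare areas of safety interest and the 180 mg group.
- **That the sponsor plans to declare safety from zero counts.** Neither document says so. The risk lies in how a table without limits will be read.

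**Conclusion.** The gap is real and moderate. The objective the protocol ranks first is reported with less statement of precision than the one it ranks below it, and the SAP omits the protocol's first-event safety summaries. Zero events in a rare category leaves true rates open up to about 0.9 per 100 PY at the most favourable exposure considered and about 3.1 at the shortest. Zero of 100 subjects leaves up to 3.6% open.

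These sizes rest on 100 patients, a common last-dose week and the SAP's exposure formula. The 180 mg figures rest on assumed group sizes. The documents give no reference rate for these events, so whether a given limit is clinically reassuring cannot be judged from them. The absence of any stated limit does not depend on these assumptions.

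**What to change.** In SAP 11.2.1, before database lock:

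- For SAEs, drug-related AEs, AEs leading to discontinuation, serious infections, adjudicated MACE and malignancies, add the number of subjects with a first event per 100 PY at risk. Censor time at the first event and give exact Poisson 95% intervals, including the upper limit when the count is zero.
- Report these in total and by the planned 90 mg / 180 mg split, stating whether the 180 mg group's time at risk includes the period before EV2.
- Add exact (Clopper-Pearson) 95% intervals to the matching subject percentages.
- Keep the event-count rates as supportive. Do not attach a simple Poisson interval to them, because repeat events within a subject are not independent.

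The cost is a separate time-at-risk derivation for each event category, since the SAP defines only one total-exposure denominator, and a few more table columns. Onset and dosing dates are already collected, and trial conduct does not change.
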